#### 14.3 **Physical Examination**

Complete physical examination should be performed at the screening, baseline, and certain subsequent scheduled visits, according to Section 12.1. A complete physical examination will include assessments of the head, ears, eyes, nose, throat, neck (including thyroid), skin/integumentary system, cardiovascular system, respiratory system, gastrointestinal system, musculoskeletal system, lymph nodes, nervous system, and extremities.

The investigator should assess all abnormal findings for clinical significance. All clinically significant abnormal findings at the screening visit will be recorded in the medical history form. Any clinically significant changes from the screening visit will be recorded as an AE.

## 14.4 Height and Weight

Height and weight will be measured, according to Section 12.1.

Subjects must weigh at least 45 kg and have a body mass index between  $\geq 18.0$  and < 30.0 kg/m^2 at both screening and baseline visits to be enrolled into this study.

# 14.5 Electrocardiogram

A 12-lead ECG will be performed and read locally according to visits specified in Section 12.1 using the ECG machine provided. ECGs will be performed in the supine position at the time points described in the Schedule of Assessments and before any scheduled vital sign measurements and blood draws. Subjects should be monitored for potentially clinically significant ECG results. Tests with abnormal results deemed clinically significant should be repeated to ensure reproducibility of the abnormality. ECG abnormalities present at screening should be recorded in the medical history form. Any abnormalities considered by the investigator clinically significant after the screening visit are to be recorded as AEs and discussed with the medical monitor, as needed.

# 14.6 Clinical Laboratory Evaluation

The hematology laboratory analyses, clinical chemistry laboratory analyses, and urinalyses will be performed at the clinical site. Reference ranges will be supplied by the local laboratory and used by the investigator to assess the laboratory data for clinical significance and pathological changes.

The investigator or medically qualified sub-investigator must review and evaluate laboratory values for each subject promptly. For each out-of-range laboratory result, the investigator or designee will evaluate whether he/she considers it clinically significant, defined as meeting at least 1 of these conditions:

- The abnormality suggests a disease and/or organ toxicity, or
- The abnormality is of a degree that requires additional active management, e.g., discontinuation of the drug, close observation, more frequent follow-up assessments, or further diagnostic investigation.

If the investigator observes a clinically significant laboratory result, the test will be repeated soon, and the subject will be monitored until the value returns to normal and/or an adequate explanation for the abnormality is found.

Investigators also may repeat specific laboratory test(s) or procedure(s) where the investigator suspects an inaccuracy or false result and that may affect the safety of the subject or interpreting the study results, only after discussion with medical monitor.

All clinically significant out-of-range laboratory values at the screening visit will be recorded in the medical history form (report a diagnosis rather than the laboratory value). All clinically significant out-of-range laboratory values after the screening visit are to be reported as an AE if this abnormality was not present at the screening visit or is assessed as having worsened since the screening visit (i.e., changed significantly from the screening visit). The investigator should diagnose an AE when reporting the abnormal laboratory value.

Subjects should be reminded to be well hydrated before all visits for phlebotomy. Subjects should fast for at least 8 hours before the visits when blood chemistry testing is planned, except for the screening visit. The screening visit laboratory values must be available before the baseline visit. Laboratory testing conducted in a non-fasting state will not be a protocol deviation.

This document is confidential.

The total blood volume to be drawn will remain below the limits defined in the (Guideline 2009).

Additional samples may be required if medically indicated (e.g., when an abnormal laboratory value is observed and requires a re-test).

See Section 14.7, Section 14.8, and Section 14.9 for details regarding pregnancy testing, virology, and TB testing samples, respectively.

The following laboratory safety tests will be performed as specified in Section 12.1.

## 14.6.1 Hematology

Hemoglobin, hematocrit, white blood cell count (with differential including eosinophils), red blood cell count, platelet count, and mean cell volume.

# 14.6.2 Clinical Chemistry

Creatinine, AST, ALT, gamma glutamyl transferase, alkaline phosphatase, lactate dehydrogenase, total bilirubin, direct bilirubin, albumin, total protein, uric acid, sodium, potassium, calcium, chloride, glucose, urea, total cholesterol, triglycerides, low-density lipoprotein, high-density lipoprotein, creatine phosphokinase (CPK). CPK isoenzyme test will be performed only if CPK is elevated to  $> 2.5 \times$  upper limit of normal (ULN). The investigator should also contact the medical monitor in such situations.

For postmenopausal subjects (i.e., absence of menstrual bleeding for 1 year before the screening visit), postmenopausal status will be confirmed with a high FSH level in the postmenopausal range.

# 14.6.3 Urinalysis

pH, glucose, ketones, blood, protein, leukocytes, nitrites, bilirubin, urobilinogen, and specific gravity.

# 14.7 Pregnancy Testing

All women of childbearing potential (WOCBP) will have a serum pregnancy test at the screening visit and urine pregnancy tests (UPTs) at subsequent visits according to Section 12.1. Pregnancy test results must be available before the administration of the study drug.

Subjects with a positive serum pregnancy test result at screening must not be enrolled.

UPTs with a sensitivity < 25 IU/L will be provided to the study centers for the study.

UPTs will be performed at the study centers, and all other samples will be sent to local laboratory for analysis.

If the result of a UPT is positive, it must be confirmed with a serum pregnancy test. Subjects with a positive serum pregnancy test result during the study must be withdrawn from the study.

## 14.8 Virology

Virology including HBsAg, HBcAb, HCV, HIV-1 and HIV-2 antibodies will be assessed at the screening visit. Subjects with a positive HBcAb and a negative HBsAg can be included if the hepatitis B surface antibody is positive (considered immune after a natural infection). Subjects who are positive for HCV antibody and negative for HCV RNA can be included.

## 14.9 **Tuberculosis Testing**

Immunosuppressant biologic treatments have been shown to increase the risk of TB infection or to cause conversion from latent to active TB sometimes. Because of this, subjects will be screened for active or latent TB before entry into this study.

#### 14.9.1 **Definitions**

Active TB is a disease caused by Mycobacterium tuberculosis in any part of the body and that is in an active state as determined by either a smear or culture taken from any source in the person's body which tests positive for TB or by radiographic evidence. Individuals with active TB are symptomatic, depending upon the location of the disease (most commonly in the lungs but also possibly in the brain, kidneys, spine, or elsewhere), and can spread the infection to others.

Latent TB is said to exist when an individual is infected with Mycobacterium tuberculosis, as evidenced by a positive Interferon Gamma Release Assay (Mazurek 2010), such as QuantiFERON-TB Gold, but is asymptomatic and has no evidence of active infection on screening pathology or radiographic tests. Such individuals do not pass the disease to others and should commence a course of prophylactic antimycobacterial treatment to eliminate the infection and commit to completing the course of treatment.

## 14.9.2 **Tuberculosis Screening**

Ideally, as part of the medical history, the subject should be asked if they have presented with active or latent TB in the past and whether they have received a bacillus Calmette-Guérin vaccination. They should also be asked if they have been in contact with any individuals known to have active TB or been placed in any circumstances that may have exposed them to an increased risk of TB infection, such as travel to TB endemic regions, close contact with persons with active TB, or workplace risk (e.g., prison, hospitals).

A subject who tests positive for latent TB (with a positive QuantiFERON-TB Gold test) should be referred to the subject's treating physician for follow-up unless the subject has a documented history of completion of an appropriate TB treatment regimen with no history of re-exposure to TB since her/his treatment was completed. If the result is indeterminate, the test may be repeated once.

This document is confidential.

If confirmed indeterminate, the subject should then be managed as though he/she has a positive test result.

## 14.10 Adverse Events

Adverse Event Definition: An AE is defined as any untoward medical occurrence in a clinical study subject administered a medicinal product which does not necessarily have a causal relationship with this treatment. An AE can therefore be any unfavorable and unintended sign (including an abnormal laboratory finding), symptom, or disease temporally associated with using a medicinal (investigational) product, whether or not it is related to the medicinal (investigational) product. This includes an exacerbation of pre-existing conditions or events, intercurrent illnesses, drug interaction, or the significant worsening of the indication under investigation not recorded elsewhere in the eCRF under specific efficacy assessments.

# Note(s):

- Any new sign or symptom reported by the subject that appears after accidental or intentional overdose or misuse of study drug should be reported as an AE.
- A diagnosis should be reported on the AE Form, instead of signs, symptoms, or abnormal laboratory values.
- Pregnancy is not to be considered an AE; however, it must be monitored and reported as described in Section 14.10.5.
- Each worsening of a chronic disease from the screening visit should be reported as a new AE.

The investigator or designee will report all AEs that occur from the time the ICF is signed until the end of the study. The Sponsor/CRO should be informed if the investigator learns of any safety information that appears to be drug-related, even after the subject has completed the clinical study.

At each post enrollment visit, the investigator (or sub-investigator) will question the subject about AEs using an open non-persuasive question to elicit reporting of AEs (for example, "Have you noticed any change in your health since the last visit?"). Directed questioning and examination will then be performed.

Any AE during the AE reporting period, whether it is related to the study drug(s) or not, will be recorded immediately in the source document and described on the AE Form along with the date of onset, severity, relationship to the study drug(s), and outcome, omitting no requested and known information. Additional information will be requested under certain circumstances.

AEs assessed as related to the treatment or study procedure will be monitored until they have resolved or reached a stable condition. Other AEs will be monitored until the last visit if they have not resolved or reached a stable condition.

The investigator will obtain and maintain in the subject's files all pertinent medical records, information and medical judgment from colleagues who assisted in the treatment and follow-up of

the subject. If necessary, the investigator will contact the subject's personal physician or hospital staff to obtain further details.

**Assessment of Severity:** Each AE will be assigned a category by the investigator:

- **Mild:** An AE easily tolerated by the subject, causes minimal discomfort, and does not interfere with everyday activities.
- **Moderate:** An AE sufficiently discomforting to interfere with normal everyday activities; intervention may be needed.
- **Severe:** An AE that prevents normal everyday activities; treatment or other intervention usually needed.

If there is a change in severity of an AE, it must be recorded as a separate event.

Assessment of Causality: The investigator is to determine whether there is a reasonable causal relationship between the AE and exposure to the study drug (i.e., nemolizumab or placebo) and/or study procedure (e.g., injection, topical background therapy, blood sample collection). Medical judgment should determine the relationship, considering all relevant factors including the pattern of the reaction, temporal relationships, relevant medical history, and confounding factors such as co-medication or concurrent diseases.

The expression "reasonable causal relationship" conveys in general there are facts or arguments to suggest a causal relationship (ICH E2A, Section IIIA 1).

The relationship assessment for an AE is to be completed using these definitions as a guideline for all AEs during this clinical study:

**Reasonable Possibility:** According to the reporting investigator, there is a reasonable possibility (i.e., suggestive evidence or arguments) there is a causal relationship despite the dose administered:

- Between the study drug and the AE, and/or
- Between the clinical study protocol procedure (e.g., injection, topical background therapy, blood sample collection) and the AE

**No Reasonable Possibility:** No suggestive evidence or arguments can be identified regarding a causal relationship between the study drug or the clinical study protocol procedure and the AE.

**Action Taken:** The investigator will describe the action taken in the appropriate section of the eCRF:

- None
- Study drug stopped
- Study drug temporarily interrupted
- Concomitant medication (any additions or discontinuations)

[figure not shown]
Other, specify

**Follow-up of Adverse Events:** All investigators should follow-up with subjects with AEs until the event is resolved or until, in the opinion of the investigator, the event is stabilized or determined to be chronic. Details of AE resolution must be documented in the eCRF.

**Documentation and Reporting of Adverse Events:** AEs should be reported and documented under the procedures outlined below. All AEs during the study must be documented on the relevant eCRF pages. The following data should be documented for each AE:

- Description of the symptom event
- Classification of "serious" or "not serious"
- Severity
- Date of first occurrence and date of resolution (if applicable)
- Action taken
- Causal relationship
- Outcome of event (unknown, recovered, not yet recovered, recovered with sequelae, death [with date and cause reported])

CC

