### 7.2 Study Rationale

During the course of development, nemolizumab in an auto-injector (AI) has been introduced. The AI is a fully disposable, single-use and single-dose injection system intended for subcutaneous injections (see Section 11.1). The AI facilitates subcutaneous injections by patients or caregivers and is the intended presentation for commercial use.

The AI is assembled around a dual-chamber cartridge, containing the same nemolizumab formulation as the DCS. To use information gathered from the DCS development program for support of a marketing authorization application with an AI, a gap analysis was performed in accordance with the Food and Drug Administration (FDA) draft guidance "Bridging for Drug-Device and Biologic-Device-Combination Products". Further chemistry, manufacturing and control data will be generated based on the information identified in the gap analysis. In addition, the current PK study will address the impact of changes in in the drug delivery parameters between AI and DCS (i.e. injection depth, injection angle and injection time)

The bridging strategy includes this PK study to assess the relative bioavailability of a subcutaneous dose of nemolizumab when administered with an AI in comparison to a DCS. The primary objective of this study is to compare the rate ( $C_{max}$ ) and extent (AUC) of absorption of a single 60-mg dose of nemolizumab administered with AI (test) versus DCS (reference) under controlled conditions in healthy adult subjects. The secondary objectives are to assess the safety and immunogenicity of nemolizumab following administration with AI or DCS in healthy adult subjects.

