### 9 INVESTIGATIONAL PLAN

### 9.1 **Description of Overall Study Design and Plan**

This is a randomized, multicenter, open-label, single-dose, parallel-group study in healthy adult subjects aged 18 to 65 years to assess the relative bioavailability of a 60-mg subcutaneous dose of nemolizumab administered with AI compared to DCS, stratified by injection site. The 60-mg dose will be administered as 2 successive subcutaneous injections of 30 mg (AI or DCS).

The study duration will be up to 16 weeks and consists of an up to 28-day screening period and a 12-week PK evaluation period.

The screening period will evaluate subject eligibility. At baseline, approximately 192 subjects will be randomized 1:1 to receive 60 mg nemolizumab delivered with either AI or DCS. Subjects will be further randomized 1:1:1 to receive injection in 1 of 3 injection sites, i.e., abdomen, front upper thigh, or outer upper arm. Approximately 32 subjects in each delivery group will be assigned to each injection site.

Subjects will receive a 60-mg dose of nemolizumab via 2 subcutaneous injections of 30 mg nemolizumab. Injections should be administered at the same location (i.e., abdomen, front upper thigh, or outer upper arm) and the same side with injection sites at least 1 inch (2.5 cm) apart. Blood samples will be collected before and after nemolizumab administration for up to 12 weeks postdose for determining the complete serum PK profile of nemolizumab.

[figure not shown]
A total of 21 blood samples will be collected, i.e., 1 before and 20 after nemolizumab administration (i.e., pre-dose, 12 hours, 24 hours, 3, 4, 5, 6, 7, 8, 9, 10, 11, 15, 22, 29, 36, 43, 50, 57, 71, and 85 days post-dose). Subjects will be confined to the study center for 1 night, from nemolizumab dosing (Day 0) to the morning after nemolizumab dosing (Day 1).

Refer to Figure 2 for an overview of the study design.

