## 17 STATISTICAL ANALYSIS

A statistical analysis plan will be prepared after the protocol is approved. This document will explain the definition of analysis variables and analysis methodology to address all study objectives. The statistical analysis plan will serve as a compliment to the protocol and supersedes it if differences occur.

The statistical evaluation will be performed using SAS® software version 9.4 or higher (SAS Institute, Cary, NC). All data will be listed. All primary and secondary efficacy endpoints, and safety endpoints will be summarized. Summary statistics will be presented by treatment group. For continuous variables, data will be summarized with the number of subjects (N), mean, standard deviation, median, minimum, and maximum by treatment group. For categorical variables, data will be tabulated with the number and proportion of subjects for each category by treatment group.

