# 17.4 Safety Analysis

**Adverse Events:** All reported AEs will be coded using the most recent version of MedDRA. TEAEs, defined as those AEs after the first administration of study treatment until last study visit, will be tabulated in frequency tables by System Organ Class and Preferred Term. Additional summary tables will be provided for SAEs, AEs related to the study drug(s) (reasonable possibility, no reasonable possibility), AEs related to the study procedure, AESIs, and AEs leading to treatment discontinuation and study withdrawal. For an AE, a subject will be counted once even if he/she has experienced multiple episodes of that AE.

Pretreatment AEs will be listed separately.

Clinical Laboratory: Laboratory data (absolute values and change from baseline) will be summarized by visit and treatment group. In addition, the number and percentage of subjects below, within, and above the laboratory reference ranges and the number and percentage of subjects who met criteria of potential clinically significant value will be summarized by treatment group. Shift tables will be generated using the reference ranges. Reference ranges will be provided in the laboratory manual.

**Vital Signs:** All vital signs and weight data (absolute values and change from baseline) will be summarized by visit and treatment group. In addition, the number and percent of subjects with clinically significant abnormal values (of clinical concern as identified by the investigator) will be summarized by treatment group.

**12-Lead Electrocardiogram:** The number and percentage of subjects with ECGs that are abnormal/clinically significant and abnormal/not clinically significant will be displayed by treatment at each visit.

**Concomitant Medications:** Prior and concomitant medications will be coded according to the most recent version of the World Health Organization Drug Dictionary Enhanced for Concomitant Medication and summarized.

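### The AE causality item pools the injection with blood sampling, so the procedure-related AE table is diluted and cannot attribute events to the injection or device

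*Protocol*

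**What the plan says.** The causality assessment in Section 14.10 offers two relationships. One is to study drug, described as nemolizumab or placebo. The other is to "study procedure (e.g., injection, topical background therapy, blood sample collection"). The definition of a reasonable possibility repeats the pooled wording: "Between the clinical study protocol procedure (e.g., injection, topical background therapy, blood sample collection) and the AE". The definitions apply to all AEs in the study, and the visible text has no separate injection or device relationship.

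Section 17.4 has TEAEs "tabulated in frequency tables by System Organ Class and Preferred Term", with additional summaries for drug-related AEs and for "AEs related to the study procedure, AESIs, and AEs leading to treatment discontinuation and study withdrawal". Section 17 adds: "Summary statistics will be presented by treatment group".

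On the design, Section 7.2 says the AI is built around a cartridge "containing the same nemolizumab formulation as the DCS" and that "the current PK study will address the impact of changes in in the drug delivery parameters between AI and DCS", naming injection depth, angle and time. Section 9.1 gives every subject the same 60 mg dose and one sampling schedule: "A total of 21 blood samples will be collected, i.e., 1 before and 20 after nemolizumab administration". Section 8.1.2 makes safety after AI or DCS administration a secondary objective, and Section 7.4 names injection-related reactions as a risk.

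**The concern.** Drug, formulation and dose are common to both arms; the device and how it delivers the injection are what is randomised. For a safety objective framed as AI versus DCS, the attribution of most interest is therefore to the injection or device. The causality item places that attribution with venepuncture, which every subject undergoes repeatedly on the same schedule whichever device was used.

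Part of the wording does not fit this study at all. It is open-label, every subject receives nemolizumab, and no topical background therapy is given, yet both placebo and topical background therapy are named.

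The item also determines what is collected. If the investigator ticks a single procedure box, no later analysis can recover whether the injection or the blood draw was meant. Preferred Terms separate events coded to a site, but presyncope, nausea, arm pain or bruising carry no such label, and one third of subjects are injected in the outer upper arm. At stake is a noisier and less interpretable safety table. The primary PK analysis is not affected.

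**Working it through.** The plan states no AE rate and no power for safety, so there is no figure to reproduce. The check asks how far pooling weakens the by-arm contrast.

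**Inputs from the protocol:** about 96 subjects per arm (Sections 9.1 and 17.1); the same blood-sampling schedule in both arms (Section 9.1).

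**Inputs assumed:** risk *p* of at least one device-related AE, 15% with AI and 5% with DCS; risk *q* of at least one blood-draw AE, equal in both arms, independent of *p*, ranging from 10 to 30%.

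**Formula.** The risk of appearing in the pooled procedure table is 1 − (1 − *p*)(1 − *q*). The risk difference is therefore

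(1 − *q*)(*p*_AI − *p*_DCS).

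Pooling multiplies the difference by (1 − *q*). It does not change its sign or create one where none exists.

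| *q* | AI | DCS | Difference | Ratio |
|---|---|---|---|---|
| 0 (separated) | 15.0% | 5.0% | 10 points | 3.00 |
| 10% | 1 − 0.85×0.90 = 23.5% | 1 − 0.95×0.90 = 14.5% | 9 points | 1.62 |
| 20% | 1 − 0.85×0.80 = 32.0% | 1 − 0.95×0.80 = 24.0% | 8 points | 1.33 |
| 30% | 1 − 0.85×0.70 = 40.5% | 1 − 0.95×0.70 = 33.5% | 7 points | 1.21 |

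The difference falls by 10 to 30% of its value. The ratio falls more steeply because equal background is added to both arms.

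**Precision.** The added background also increases variance. As a gauge only, a two-sided 5% normal-approximation comparison at 96 per arm would have power 0.64 when separated and 0.36, 0.23 and 0.17 when pooled at *q* = 10, 20 and 30%. With assumed risks of 20% and 5%, the difference goes from 15.0 points to 13.5, 12.0 and 10.5, and power from 0.89 to 0.63, 0.44 and 0.32.

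**Attribution.** Among AI subjects in the pooled table, the share with a device-related event is 0.15/0.235 = 64%, 0.15/0.320 = 47% and 0.15/0.405 = 37% at the three values of *q*. For DCS it is 0.05/0.145 = 34%, 0.05/0.240 = 21% and 0.05/0.335 = 15%. The table itself would not show which subjects these are.

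**The case against.** A reader might infer that the procedure-related table cannot show device-related harm, or that it is the only causality-based table that could. The documents support neither reading. Summaries are by randomised arm and the sampling schedule is common, so blood-draw events add the same expected background to each arm. The contrast shrinks but remains. Section 17.4 also plans a drug-related table, and Section 14.10 joins the drug and procedure relationships with and/or, so a local reaction may already be attributed to drug, procedure or both. TEAEs by Preferred Term compare the arms with no causality judgement at all, which in a randomised trial is the stronger evidence.

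Other records help too. There is one dosing occasion, AE onset dates are recorded (Section 14.10), the time and site of injection are recorded (Section 11.5.2), and most post-dose draws fall days to weeks after it. Device malfunctions and complaints have their own route (Sections 11.5 and 11.7). Section 14.10.1, to which AESI reporting refers, and one secondary endpoint are redacted, so dedicated capture of injection reactions may exist. The power figures concern a test that the protocol does not plan.

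All of this stands, and it limits the point to a minor one. Two things remain. First, near dosing, timing does not separate the causes well: the pre-dose sample is drawn before the injection at the same visit, with further draws at 12 and 24 hours. Second, the complaint route covers faulty units, not AEs after a device that worked normally. Sub-tables can be left to the SAP, but only if the form has collected the distinction.

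**Conclusion.** The point holds as a minor one. Section 14.10 pools the injection with blood sampling in one causality item, and Section 17.4 summarises that pooled item. The by-arm comparison stays unbiased. What is lost is sharpness (a risk difference of 9 to 7 points in place of 10 under the stated assumptions) and the ability to attribute an event to the injection or device, mainly for non-site-specific events around dosing. The 5%, 15% and 10 to 30% rates, the equality of the blood-draw risk across arms and the independence are all assumptions. The documents do not show that the trial cannot detect device-related harm, nor that injection reactions go uncaptured, since the redacted sections may cover them. The references to placebo and topical background therapy are wrong for this trial on any reading.

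**What to change.** In Section 14.10, and on the AE form, record three relationships separately: to study drug (nemolizumab), to injection/device (AI or DCS), and to other study procedures such as blood sampling. Allow more than one for the same event. Delete placebo and topical background therapy.

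In Section 17.4, replace the single procedure-related summary with separate summaries of injection/device-related and other procedure-related TEAEs by treatment group. A further display by randomised body site is optional and could be left to the SAP.

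The cost is one more option on the form and one more table. Some events will be hard to attribute; allowing more than one relationship handles most of these. The form change has to precede AE collection, because the distinction cannot be reconstructed from a pooled answer.
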